4.0 STUDY DESIGN

General Design

This is a pilot study of utilizing SPECT/CT imaging with 99m Tc-SC to accurately identify and quantitate functional liver tissue on serial imaging in patients receiving RT or surgery for liver cancer. The long-term goals are to use functional imaging to improve risk stratification for selecting which patients should undergo aggressive local treatments with RT or surgery and to aid in RT planning by preferentially sparing functional liver tissue, thereby leading to reduced liver toxicity. There will be two cohorts of patients: those receiving RT (Cohort A) and those undergoing surgery (Cohort B). A total of 60 patients will be enrolled (Cohort A, n = 40; Cohort B, n = 20).

All patients will have a total of 3 SPECT/CT imaging with ^{99m}Tc-SC. The first scan in both cohorts will be routine medical care (not experimental) and will take place prior to initiation of RT or surgery. Two follow up scans will be part of the protocol. In cohort A, the first follow up scan will occur at mid-RT, and the second one about 1 month post-RT (prior to any potential anatomical liver changes). In cohort B, the first follow-up scan will occur 3-5 days postoperatively (prior to any potential liver hypertrophy), and the second one about 1 month post-operatively (when liver hypertrophy is expected to occur).

Endpoints

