As a validation step, these baseline SC imaging data will be correlated to indocyanine green (ICG) clearance in patients (in those who opt to undergo this study), which assesses liver function based on the rate of clearance of a contrast agent over serial blood draws, and is considered a standard assessment of global liver function. ICG is a water-soluble compound that is selectively taken up by hepatocytes and transported into the biliary system without undergoing metabolism [37]. ICG clearance, therefore, can be utilized as an index of functioning hepatocyte mass [38] and is correlated with prediction of liver dysfunction and mortality associated with surgical resection [39]. The retention rate of ICG 15 minutes after administration (ICG-R15), a ratio of the ICG concentration at 15 minutes to its initial concentration in the blood, will be used to benchmark SC uptake metrics against. Higher ICG-R15 rates indicate worse liver function and would be expected to be correlated with lower global SC uptake metrics.

Functional FLR will be generated by calculating the volume of liver within the optimal image threshold as defined above. Anatomic FLR will be delineated and calculated on CT or MRI images using portal and hepatic veins as landmarks for segmental division. Logistic regression analyses and Pearson chi-square test will be used to compare the ability to predict for PHLR between functional FLR and anatomic FLR.

b) Correlate *post-treatment* changes in SC uptake on SPECT/CT imaging with changes clinical liver function. Relative changes in the parameters identified at baseline will be tested for correlation to changes in clinical liver function, including CTP score and ALBI grade, as well as their individual constituents.

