4.2.1 Primary Endpoints

a) Significant differences in Wilcoxon rank sum of ROC-optimized SC SPECT parameters will be tested between CTP classes. Spearman rank correlations between optimal SC SPECT parameters and clinical liver function parameters will be tabulated for the following categories: (1) composite liver function scoring systems (CTP score, ALBI grade), (2) individual quantitative liver function components (albumin, bilirubin, INR), and (3) individual qualitative clinical liver function components (encephalopathy, portal hypertension, ascites, and splenomegaly). Qualitative components will be treated as binary categorical variables (yes/no). Imaging and clinical parameters of liver function will be tested for association with overall survival. Continuous variables will be dichotomized above and below a threshold value that maximized accuracy of classification under ROC with balanced sensitivity and specificity. Univariate Cox proportional hazard regression will then be performed on all continuous and categorical variables. Statistically significant variables will serve as inputs into multivariate Cox proportional hazard regression. A stepwise backwards variable selection procedure will be followed to remove non-significant variables with high cross-correlation until the model log-likelihood is maximized.

Because radiomics generates feature sets of ~50 metrics, machine learning methods will be utilized to develop predictive models that are robust against overfitting, utilizing feature selection and classification/regression methods such as support vector machines, Bayesian analysis, and decision trees. These machine learning methods will be compared against standard statistical methods, such as ROC analysis and Kaplan-Meier estimation / Cox regression, for association to clinical liver function, prior liver-directed therapies, clinical outcomes (i.e. survival), and toxicity (i.e. CTP score progression).

b) The same set of statistical analysis will be performed for association of post-treatment changes in SC uptake on SPECT/CT imaging to clinical endpoints. Machine learning methods will test whether post-treatment changes in SC SPECT/CT provide independently predictive information after adjusting for baseline parameters.

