Serum Pregnancy Test††	Х			
ICG Clearance Test†		X*	X*	X*
CT or MRI scan∥	Х			X
99mTc-SC SPECT/CT scan + IV contrast enhanced abdominal CT scan		Χ¶	X*	X*

^{*}Denotes a research procedure; all others are standard of care.

Imaging Protocol

SPECT/CT with ^{99m}Tc-SC will be performed per standard protocol, which is currently in routine clinical use. The protocol will consist of a SPECT/CT image acquisition on a dual head gamma camera and 16 slice CT scanner. Following the injection of 7 mCi (259 MBq) [99mTc] sulfur colloid, SPECT scans will be acquired 15 minutes post-injection over a fixed time-averaged frame (64 views, 20 sec/view, 180 degree arc). Emission images will be corrected for scatter, collimator-detector response, and attenuation using a tidal breathing end-exhale position CT image. Reconstructions will be performed with a variant of ordered subset expectation-maximization (OSEM) iterative algorithm. An initial baseline scan prior to RT or surgery will identify areas of functional liver. In the radiation therapy cohort, this scan will be in the radiation treatment position which can be fused precisely with the

[†]On the same day as ^{99m}Tc-SC SPECT/CT scans +/- 2 days.

^{**}Complete blood count, complete metabolic panel, prothrombin time, partial thromboplastin time, AFP (for hepatocellular carcinomas), CA19-9 (for cholangiocarcinomas or metastatic pancreatic cancer), CEA (for metastatic colon cancer), CA-125 (for metastatic ovarian cancer). For patients receiving SBRT, patients will have blood drawn after fraction 3 +/- 1 fraction. For patients receiving proton beam therapy patients will have blood drawn every 7 days +/- 3 days

^{††}For women of child bearing potential only.

Type of scan is up to the discretion of treating physician.

[¶]At the time of simulation for RT planning.

[†]On the same day as 99mTc-SC SPECT/CT scans +/- 2 days.

^{**}Complete blood count, complete metabolic panel, prothrombin time, partial thromboplastin time, AFP (for hepatocellular carcinomas), CA19-9 (for cholangiocarcinomas or metastatic pancreatic cancer), CEA (for metastatic colon cancer), CA-125 (for metastatic ovarian cancer).

^{††}For women of child bearing potential only.

Type of scan is up to the discretion of treating physician.

[¶]Within 2 weeks prior to surgery.

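### ALBI enters the correlation and change analyses only as a grade; the continuous ALBI score and its change would be a stronger variable at no cost

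*Combined protocol and SAP*

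**What the plan says.** Section 4.1.1 (b) relates imaging change to change in clinical liver function, "including CTP score and ALBI grade, as well as their individual constituents". The list is open-ended. CTP appears as a score and ALBI only as a grade.

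Section 4.2.1 (a) sets the method: "Spearman rank correlations between optimal SC SPECT parameters and clinical liver function parameters will be tabulated". Its first category of clinical parameters is "composite liver function scoring systems (CTP score, ALBI grade"; its second is "individual quantitative liver function components (albumin, bilirubin, INR". Section 4.2.1 (b) carries the method over to change: "The same set of statistical analysis will be performed for association of post-treatment changes in SC uptake".

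No continuous ALBI score is named anywhere, and no reason is given for preferring the grade. The study calendar in section 7.0 schedules standard liver function blood tests at all three scan times in both cohorts. The footnote lists "Complete blood count, complete metabolic panel, prothrombin time, partial thromboplastin time" among them.

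On sample size, section 4.0 states: "A total of 60 patients will be enrolled (Cohort A, n = 40; Cohort B, n = 20". The documents contain no power calculation, alpha or target correlation.

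**The concern.** A grade moves only when a patient crosses a cut-point. The first follow-up scan is mid-radiation or 3–5 days after surgery, and sections 4.0 and 7.0 put the second at about one month. (Section 4.1.2 gives 6 months for the later Cohort B scan; this point does not depend on that difference.) Over such intervals many patients probably stay in the same grade, even when albumin and bilirubin have moved. Those patients share one tied rank, and a Spearman test learns little from them.

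This matters because section 3.1 (b) hypothesises that imaging change predicts liver toxicity earlier than clinical assessment does. Small early changes are therefore the signal of interest. A real association with the ALBI composite could look weak or absent only because the composite was banded before it was correlated.

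**Working it through.** The plan has no figure of its own to reproduce. The sample sizes (40 and 20) and the Spearman test come from the documents. Everything else is assumed, including that the ALBI grade is a banding of a continuous score built from albumin and bilirubin, since the documents do not define ALBI.

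**1. Anchor for the continuous score.** The Fisher approximation is power ≈ Φ(atanh(r)·√(n−3) − 1.96), two-sided 5%. At r = 0.5:
- n = 40: 0.549 × 6.083 − 1.96 = 1.38, so power is about 92%.
- n = 20: 0.549 × 4.123 − 1.96 = 0.30, so power is about 62%.

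The formula is for a Pearson correlation. Simulated Spearman power is slightly lower: 88–90% and 55–58%.

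**2. Score against grade, by simulation.** Assumptions: three grades, middle grade 1.2 units wide; normal baseline score with SD 0.5, centred on a boundary (which favours the grade); normal change with mean zero and SD 0.2–0.4; true correlation r between imaging change and score change; two-sided 5%.

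About 76–87% of patients then show no grade change, so 13–24% do change. That is 0.13 × 40 ≈ 5 to 0.24 × 40 ≈ 10 patients in Cohort A, and about 3 to 5 of 20 in Cohort B.

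**3. What the planned constituents recover.** In the same set-up the score is two equally weighted continuous constituents, correlated 0 or 0.28 with each other. Each is tested separately, and success means either is significant after Bonferroni correction.

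| n | r | Score | Grade | Two constituents, Bonferroni |
|---|---|---|---|---|
| 40 | 0.4 | about 66–70% | about 16–31% | about 48–59% |
| 40 | 0.5 | about 88–89% | about 25–47% | about 68–80% |
| 20 | 0.4 | about 36–41% | about 8–16% | about 24–30% |

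At n = 40 the shortfall of the constituents against the score is about 8–21 points. Without multiplicity correction (the plan specifies none) it is about 0–7 points, but the error rate is then inflated.

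**4. Sensitivity.** The assumptions were widened to three baseline splits (33/33/33, 50/45/5 and 70/27/3%), four SDs of change (0.25 to 1.0 baseline SD) and three mean shifts (0, 0.5 and 1 SD of change): 3 × 4 × 3 = 36 scenarios, all at r = 0.5.
- No grade change: 45–92% of patients, and more than half in 34 of the 36.
- Power at n = 40: 16–65% with grade change, 88–90% with score change.
- Power at n = 20: 5–35% with grade change, 55–58% with score change.
- One continuous constituent correlating 0.8 with the score: 67–71% at n = 40 and 36–39% at n = 20.

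The grade was weaker than the score in every scenario. The direction is stable; the size is not.

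These calculations concern change. The smaller question of grade against score at baseline was not quantified.

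**The case against.** The strongest reply is that ALBI grade is one entry among several. The sentence that names it also names CTP score and the constituents, and section 4.2.1 correlates albumin, bilirubin and INR as quantities. Optional ICG clearance is repeated at each scan as well. A reader might infer that clinical change is measured by ALBI grade alone, or that objective (b) as a whole loses the full gap between score and grade. The documents support neither reading, because the constituents recover much of the loss.

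The reply does not dispose of the point. Two separate tests split one composite signal, and with correction they fall somewhat short of the score.

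A second reply is that this is a single-arm pilot whose correlations are to be tabulated, that the list is open-ended, and that a score could be computed later from the same blood values. That is fair and keeps the severity low. But an open list commits nobody to the score, and adding it after the results are seen would be a post hoc choice.

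**Conclusion.** The point stands in a limited form. ALBI is planned only as a grade, and change in that grade is likely to be a poor variable for a Spearman test in cohorts of this size. The loss is confined to the ALBI composite. The fair measure of what the plan forgoes is the modest gap between the score and the separately tested constituents, not the large gap between score and grade.

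All of these sizes rest on assumed cut-points, SDs and correlations. A reader might also take it as established that most patients will show no grade change. The documents give no proportion changing grade and no SD of change, so this is a likely consequence and not a fact. Severity is minor: a free improvement to an exploratory analysis.

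**What to change.** In sections 4.1.1 and 4.2.1, name the continuous ALBI score, and its change from baseline, as the ALBI variable in the correlation and change analyses. State the formula used. Keep ALBI grade, and shifts between grades, for description. Leave CTP score and the individual constituents as planned.

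The cost is a few words. The score uses albumin and bilirubin, which the plan already intends to analyse, from blood tests already scheduled with each scan. No extra sample, visit or patient is needed.

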4.1.2 Secondary Endpoints

Patients will receive two follow-up SC SPECT/CT scans: mid-radiation treatment (cohort A) or 3-5 days post-surgery (cohort B) and 1 month (cohort A) or 6 months (cohort B). For the second aims (a) and (b) looking at liver tissue inside the radiation field, the images will be processed similarly to the primary endpoints. Regional functional liver changes from scatter, collimator, and attenuation-corrected SPECT/CT images will be modeled as a function of regional radiation dose. Three types of dose-response models will be defined to predict changes in liver function status:

Dichotomous dose-response (complete function loss): Single dose thresholds on co-registered baseline and post-treatment SPECT/CT will be applied to investigate a binary threshold for functional loss. Image voxels exposed to a radiation dose above the selected threshold will be excluded when calculating the percent change in function liver image parameters. The product of functional liver remnant following complete loss of function on imaging (post-to-pre-treatment ratio) and baseline liver function status (e.g. ICG clearance, bilirubin, etc.) will be compared to the repeat functional liver status measured post-RT.

Binned dose-response (partial function loss): Dose threshold bins will be co-registered to the baseline and post-treatment SPECT/CT in order to explore different thresholds of radiation leading to partial loss in lung function. For imaging voxels in each dose bin, the corresponding SC SPECT/CT uptake decline will be calculated following a count normalization outside the radiation field. Model-predicted change in

SC SPECT/CT image parameters will be compared against the measured change post-therapy. The product of functional liver remnant following partial loss of function on imaging (post-to-pre-treatment ratio) and baseline liver function status (e.g. ICG clearance, bilirubin, etc.) will be compared to the repeat functional liver status measured post-RT.

Continuous dose-response (function loss distribution): The continuous dose distribution will be coregistered to the baseline and post-treatment SPECT/CT. The relationship between dose and SC SPECT/CT uptake reduction at the voxel scale will be directly characterized via linear and logistic regression methods with noise suppressing fitting techniques (multiscale lung \rightarrow lobar \rightarrow voxel model). Goodness of model fits (pseudo R^2) using rigid and deformable registration of SPECT/CT images and RT dose will be compared. The product of functional liver remnant from the function loss distribution on imaging (post-to-pre-treatment ratio) and baseline liver function status (e.g. ICG clearance, bilirubin, etc.) will be compared to the repeat functional liver status measured post-RT.

Statistical Analysis

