3.0 STUDY OBJECTIVES

3.1 Primary Objectives

- a) Develop new quantitative metrics of baseline SC uptake on SPECT/CT imaging and correlate with clinical parameters of liver function and clinical outcomes in liver cancer patients receiving RT or surgery.
 - Hypothesis: Global metrics of baseline pre-treatment SC uptake on SPECT/CT imaging are more predictive for survival than conventional clinical measures of liver function and are associated with ICG clearance. For patients receiving surgery, the volume of the future liver remnant (FLR) as defined by SC SPECT/CT imaging (functional FLR) is more predictive for PHLF than CT-defined FLR volumes. Heterogeneity metrics of baseline SC uptake are associated with the severity of cirrhosis and prior liver-directed therapy; specifically, SC uptake within the liver is more heterogeneous in less compensated livers and in those that have received a higher number of liver-directed therapies.
- b) Correlate *post-treatment* changes in SC uptake on SPECT/CT imaging with changes clinical liver function.

Hypothesis: Changes in SC uptake between pre-RT and mid-RT/post-RT SPECT/CT scans are associated with changes in clinical liver function in response to RT and are predictive of liver toxicity at earlier time points compared to clinical assessments of liver function. SC uptake in the FLR (non-treated) is stable and preserved over time between pre-surgery and immediately post-surgery (3-5 days postoperative) scans.

Secondary Objectives

- a) Estimate the dose response relationship on multiple spatial scales (global liver, regional liver, liver image voxel) between radiation dose and changes in SC uptake, both acutely (mid-RT) and subacutely (1 month post-RT), using SC SPECT/CT imaging.
 - Hypothesis: Deficits in SC uptake due to absorbed dose is governed by a linear dose relationship. As the dose delivered to the region/voxel increases, the uptake in SC decreases in a linear fashion.
- b) Estimate the degree of radiation response in liver tissue with varying levels of function (i.e. compare radiation dose response of well compensated livers against less compensated livers).

This may establish a threshold of liver tissue that would be "safe" to treat without significantly affecting liver function.

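### In all three dose-response models, multiplying baseline by the post/pre functional ratio predicts a better bilirubin when liver function is lost; the ICG scale is not stated

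*Combined protocol and SAP*

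**What the plan says.** Section 4.1.2 gives the purpose of the modelling: "Three types of dose-response models will be defined to predict changes in liver function status". Each of the three models then closes with the same step. A functional remnant, expressed as a ratio of post-treatment to pre-treatment imaging, is multiplied by a baseline clinical measure, and the result is set against the repeat measurement: "post-to-pre-treatment ratio) and baseline liver function status (e.g. ICG clearance, bilirubin, etc.) will be compared to the repeat functional liver status". The binned version begins "The product of functional liver remnant following partial loss of function on imaging (post-to-pre-treatment ratio" and the continuous version "The product of functional liver remnant from the function loss distribution on imaging (post-to-pre-treatment ratio"; the dichotomous version has the same structure. ICG clearance and bilirubin are named in all three.

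Secondary Objective (a) in Section 3.0 gives the expected direction of the ratio: "As the dose delivered to the region/voxel increases, the uptake in SC decreases in a linear fashion".

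On ICG, Section 4.1.1 treats clearance as an index of working hepatocyte mass, so higher is better. The only ICG quantity it defines is the 15-minute retention ratio, for which it says "Higher ICG-R15 rates indicate worse liver function and would be expected to be correlated with lower global SC uptake metrics". The test is done only "in those who opt to undergo this study". The Cohort A calendar in Section 7.0 schedules standard serum liver tests at all three scan times.

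Section 4.2.1 lists "individual quantitative liver function components (albumin, bilirubin, INR") among the clinical measures. It covers primary endpoints only. No statistical section for the secondary endpoints says how the product is to be compared with the repeat value.

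**The concern.** A product with a ratio below 1 suits a measure that falls when function falls. Bilirubin does the opposite, so the more loss a model predicts, the better the bilirubin it forecasts. Nothing in Section 4.1.2 inverts or transforms the measure, or limits the rule to measures where higher is better.

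This matters because the product is the only stated test of the dose-response models against clinical liver function. With ICG optional, bilirubin is the named measure that most Cohort A patients can supply. There are two ways to be misled:

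- Under an agreement measure, a model that correctly predicts loss scores worse than one that predicts none.
- Under a rank correlation of product with repeat value, both sides contain the patient's baseline. Between-patient spread can then give a clearly positive coefficient that hides the wrong sign.

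**Working it through.** The plan gives no figure for this analysis to reproduce. The check is algebra on its rule, followed by an illustration.

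**Inputs.**
- From the documents: the product rule (Section 4.1.2), a ratio r below 1 when function is lost (Section 3.0), and 40 patients in Cohort A (Section 4.0).
- Outside premise: bilirubin rises as liver function worsens. This is the standard reading; the documents do not state it.
- All numerical values of r, baseline and spread are assumptions.

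**Step 1, direction.** Predicted = r × baseline. With 0 < r < 1, predicted < baseline for any positive measure. For bilirubin, that is an apparent improvement.

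**Step 2, size of the error.** If post ≥ pre and r < 1, then |post − r × pre| − |post − pre| = (post − r × pre) − (post − pre) = (1 − r) × pre. No form for the bilirubin response is assumed. At baseline 1.0 mg/dL:

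| r | Product (mg/dL) | Extra error over predicting no change (mg/dL) |
|---|---|---|
| 0.9 | 0.90 | 0.10 |
| 0.7 | 0.70 | 0.30 |
| 0.5 | 0.50 | 0.50 |

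The same algebra ranks competing models. For such a patient, the model predicting more loss is further off by the difference in ratios × baseline. For r = 0.9 against r = 0.7 this is 0.2 × 1.0 = 0.20 mg/dL.

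**Step 3, rank correlation.** Simulation with n = 40 and 4,000 replicates: log post = log pre − b × log r + N(0, SD 0.2). Varied over 18 scenarios: b = 0, 0.5, 1 (true slope of log change on log ratio 0, −0.5, −1); r uniform on 0.5–1 or 0.8–1; SD of log baseline 0.3, 0.5, 0.7.

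| Quantity | Range of mean Spearman |
|---|---|
| Product with repeat value | +0.30 to +0.94 |
| Baseline alone with repeat value | about 0.70 to 0.95 |
| Log ratio with log change | about 0 to −0.69 |

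The product correlates positively in every scenario, although the true relation of change to ratio is null or negative. Baseline alone has the higher mean in all 18, so on average the imaging ratio makes the forecast worse.

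**Step 4, ICG scale.** Assume mono-exponential clearance, R15 = exp(−15k), with baseline R15 of 20% and r = 0.7.
- Product applied to R15: 0.7 × 20% = 14%, an apparent improvement.
- Product applied to the rate: k = −ln(0.20)/15 = 0.1073 per minute; 0.7 × 0.1073 = 0.0751; R15 = exp(−15 × 0.0751) = 32.4%, a worsening.

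The rule is coherent on a clearance scale and reversed on the retention scale. The formulas do not say which one enters.

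**The case against.** **The formulas say ICG clearance, not retention.** Read plainly, the product then has the right direction, and ICG-R15 is introduced separately for the baseline benchmarking. That is a fair reading, so the ICG point is only a request to state the scale. The request stands because retention is the one ICG metric the plan defines.

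**Bilirubin is an example in an exploratory analysis, and a competent analyst would invert it.** A drafting slip is likely. But bilirubin is one of two named measures in all three formulas, and different inversions give different answers, so the choice should be written down before data are seen.

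**The comparison is unspecified, so the harms depend on statistics supplied here.** True for the size of the harm. The ratio enters in the wrong direction under either statistic.

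**Other analyses show the sign.** Sections 4.1.1(b) and 4.2.1(b) relate changes in imaging to changes in clinical function, including individual components. That limits the consequence. They use measured imaging change, though, and do not test the dose models' predictions.

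**The simulation inputs are all assumed.** Correct. The +0.30 comes from the most extreme corner (losses of 0–50%, log-SD 0.3, slope −1). With losses of 0–20%, baseline beats the product by only about 0.01 to 0.06 on average, and not in every single trial. INR is included only if the open-ended list in the formulas extends that far.

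**Conclusion.** The concern holds. Followed as written, the rule predicts a lower bilirubin whenever a model predicts loss of function, in all three models. The direction rests on the plan's formula, its own expectation of falling uptake, and the standard premise that bilirubin rises with dysfunction; it does not depend on any simulation input. The excess error of (1 − ratio) × baseline is exact for patients whose bilirubin is unchanged or rises; the documents do not say what share that will be. The correlation figures are illustrative only.

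The ICG part is an ambiguity, not an error. The effect is confined to the clinical check of secondary models in Cohort A. The imaging-based fits (predicted against measured change in the binned model, pseudo R² in the continuous one) and the primary analyses do not use the product. It should be fixed, but it does not threaten the study's main results.

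**What to change.** Revise the closing sentence of each of the three models in Section 4.1.2:

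1. State the ICG scale and restrict the product to measures that rise with function: an ICG elimination rate and albumin. The rate can be fitted from the serial draws or, assuming mono-exponential clearance, taken as k = −ln(R15)/15. For albumin this corrects only the sign; the documents do not support strict proportionality.
2. For measures that rise with dysfunction (bilirubin, ICG-R15, and INR if used), regress log(post/pre) of the measure on the log of the model-predicted ratio. State a negative slope as the expected direction and report the slope with its 95% CI. If baseline divided by the ratio is shown, label it as an assumption.
3. Name the comparison statistic and define it on within-patient change, not on the correlation of the product with the repeat value.

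The cost is three reworded sentences, with no new data or procedure. Other change-based forms would also correct the direction. Precision will be limited if losses are small: under the Step 3 assumptions with 0–20% loss, a true slope of −1 reaches significance in about 50% of runs and −0.5 in about 17%. The slope should therefore be presented as an estimate with its interval, not as a pass-or-fail test.
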